### **15.5.2. Primary Objective #2: Proliferation of Circulating T-Cells**

The second primary objective involves an assessment of whether neoadjuvant immunotherapy will increase proliferation of circulating T-cells compared to baseline measurements.

#### **15.5.2.1. Variable**

To examine T-cell proliferation rates, Ki67 staining will be performed on PD-1+/CD8+ T cells extracted both from the peripheral blood and from resected tissue.

As described in [Table 1](#) of Section [12](#), blood will be drawn longitudinally during treatment to study how a single dose of nivolumab and ipilimumab before surgery affect T-cell proliferation over time.

The primary outcome is the fold-change in Ki67 levels on peripheral-blood T cells between baseline and Day 1.

#### **15.5.2.2. Statistical Hypothesis, Model, and Method of Analysis**

As noted in Section [15.5.2.1](#), the primary outcome for each patient is the fold- change in Ki67 levels between baseline and Day 1. The mean fold- change will be tested using a one-sample t-test. If assumptions for conducting a t-test are violated, a logarithmic transformation may be considered as well as a Wilcoxon one-sample test.

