### **5.6. Data Analysis and Statistical Considerations**

Feasibility will be assessed by the proportion of patients who have their surgery delayed. With the checkpoint inhibitors being administered on Day -7, the surgery is scheduled for Week 1, Day 1 ( $\pm$  3 days). *Surgery will be considered delayed if it never occurs or occurs after Day 4 (i.e. Day 1 + 3).* The proportion of patients experiencing surgical delay as defined in Section 15.5.1.1 will be computed as the number of patients with delay divided by the total number of patients per arm. Methods developed for continuous monitoring of toxicity will assess whether the number of surgical delays is excessive. Monitoring rules based upon Pocock monitoring rules are provided in Section 15.5.1.2.

A one-sample t-test will assess whether significant changes fold-change in Ki67 levels between baseline and Day 1 occurred.

Kaplan-Meier methodology will be used to graphically display survival and progression-free survival; whereas, cumulative incidence curves will be used to graphically display time to local intracranial progression, time to distant intracranial progression, and time to overall intracranial progression as defined in Section [15.6.2](#).

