## 8. OBJECTIVES AND ENDPOINTS

	Objective	Endpoint	Analysis
Primary	Assess the feasibility of neoadjuvant ipilimumab and nivolumab treatment before surgery and SRS among patients with solid tumor brain metastases	Among eligible patients, the percentage of patients who experience surgical delay. Surgery is considered delayed if it occurs more than 10 days after ipilimumab and nivolumab, or never occurs, for reasons relating to the immunotherapy treatment.	See Section 15.5.1
Other Primary	Demonstrate that neoadjuvant immunotherapy will increase proliferation of circulating T-cells compared to baseline measurements	Mean fold-change between baseline and day 1 in Ki67 levels	See Section 15.5.2
Exploratory	Describe the survival of patients with solid tumor brain metastases receiving neoadjuvant ipilimumab and nivolumab followed by surgery and SRS.	Median survival	See Section 15.6.1
Exploratory	Describe the time to local intracranial progression	Median time to local intracranial progression	See Section 15.6.2
Exploratory	Describe the time to distant intracranial progression	Median time to distant intracranial progression	See Section 15.6.2
Exploratory	Describe the time to overall intracranial progression (local or distant)	Median time to overall intracranial progression (local or distant)	See Section 15.6.2
Exploratory	Describe progression-free survival	Median progression-free survival	See Section 15.6.2
Exploratory	Quantify the rate of radiation necrosis	Percent of patients with radiation necrosis	See Section 15.6.3
Exploratory	Describe immune express profiles	Normalized immune expression	See Section 15.6.4

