## **15.8. Sample Size Calculation**

Twenty (2) patients will be enrolled onto this study and treated with ipilimumab and nivolumab. We anticipate that due to drop-out and/or sample quality issues Ki67 data will be available from approximately 17 patients.

Kim et al (2019) [23] reports that a higher fold-change in the percentage of Ki-67+ cells among PD1+ CD8+ T cells 7 days after the first dose of anti-PD-1 therapy is associated with greater efficacy. The distribution of this fold-change is graphically presented in Figure 2A of the Kim article. Based upon a crude estimate of the value of Ki-67 associated with each data point in this figure, mean fold-changes were computed. The mean fold- change among the 11 patients with durable clinical response is 4.9 (SD=2.0; CV = 0.42); whereas the mean fold-change among the 20 patients with non-durable response is 2.5 (SD=1.3; CV=0.54). Overall, the mean fold-change is 3.4 (SD=2.0; CV=0.6).

Assuming that CV=0.6, a one-sample t-test ( $\alpha=0.05$ ; two-tailed) has >95% power to detect a mean fold- change of 1.7 among the 17 patients with evaluable Ki67 data.

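### The Ki67 primary test uses the raw mean of Day 1/baseline ratios, which exceeds 1 even when nothing changes, so it falsely declares an increase up to about three times as often as its nominal rate

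*Combined protocol and SAP*

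**What the plan says.** Section 15.5.2.1 defines the variable: "The primary outcome is the fold-change in Ki67 levels on peripheral-blood T cells between baseline and Day 1". Section 8 gives the endpoint as "Mean fold-change between baseline and day 1 in Ki67 levels". Section 15.5.2.2 names the test: "The mean fold- change will be tested using a one-sample t-test". The synopsis (section 5.6) agrees: "A one-sample t-test will assess whether significant changes fold-change in Ki67 levels between baseline and Day 1 occurred".

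The only mention of another scale is in section 15.5.2.2: "If assumptions for conducting a t-test are violated, a logarithmic transformation may be considered as well as a Wilcoxon one-sample test". The plan gives no diagnostic, threshold or order of preference for that choice. It also does not state the null value; 1, meaning no change, is the only sensible reading.

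Section 15.8 sets a two-tailed alpha of 0.05, about 17 patients with Ki67 data, a CV of 0.6, and more than 95% power for a mean fold-change of 1.7.

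**The concern.** A ratio is not symmetric about 1. A doubling (2.0) and a halving (0.5) cancel on the log scale, but their arithmetic mean is 1.25. If baseline and Day 1 values differ only by chance, the log ratio is symmetric about 0, and the mean of the ratio exceeds 1 whenever there is any variation. A test of whether the mean ratio equals 1 is then testing a null that is false when nothing has happened.

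The error runs in the direction of the trial's hypothesis. Since the randomised control was removed (sections 9.1.7 and 15.1), no comparison group would show the same drift. Feasibility has a monitoring boundary (section 15.5.1.2) but no final hypothesis test, so Ki67 is the only formally tested primary endpoint. What is at stake is a false claim that neoadjuvant treatment raised T-cell proliferation.

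**Working it through.** **Inputs.** From section 15.8: n = 17; two-sided alpha 0.05, hence 2.5% for falsely declaring an increase; CV 0.6 overall, 0.42 in durable responders and 0.54 in non-durable responders; effect 1.7. Assumed: lognormal ratios, a geometric mean of 1 under no effect, and CVs of 0.2 and 0.3 to cover smaller null variability.

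**The plan's power figure.** Noncentral t, 16 df:

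- Log scale, with 1.7 as a geometric mean: σ = √ln(1 + 0.6²) = 0.5545; noncentrality = ln(1.7)/0.5545 × √17 = 3.95; power 95.9%. This reproduces the claim of more than 95%.
- Raw scale, as section 15.5.2.2 specifies: SD = 0.6 × 1.7 = 1.02; noncentrality = 0.7/1.02 × √17 = 2.83; power 75.7%.

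Under the stated CV, the sample size statement therefore fits a log-scale analysis and not the t formula for the raw test. The formula is only approximate for skewed data: simulating the raw test on lognormal ratios gives 88.3% if 1.7 is the arithmetic mean and 98.3% if it is the geometric mean.

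**Bias under no effect.** With log ratio ~ N(0, σ²), the expected ratio is exp(σ²/2) = √(1 + CV²). At CV 0.6 this is √1.36 = 1.166.

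**False-positive rate.** 200,000 simulated trials per row, n = 17, no shift, raw t-test against 1:

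| CV | Expected ratio | Raw test, false increase | Multiple of 2.5% | Log test, false increase |
|---|---|---|---|---|
| 0.2 (assumed) | 1.020 | 3.9% | 1.6 | 2.5% |
| 0.3 (assumed) | 1.044 | 5.0% | 2.0 | 2.6% |
| 0.42 (section 15.8) | 1.085 | 6.2% | 2.5 | 2.5% |
| 0.54 (section 15.8) | 1.136 | 7.4% | 2.9 | 2.5% |
| 0.6 (section 15.8) | 1.166 | 8.0% | 3.2 | 2.5% |

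Repeat simulations at CV 0.6 gave 7.8% to 7.9%, which is Monte Carlo variation. At CV 0.6 the lower tail is 0.7%, so total rejection is 8.0% + 0.7% = 8.7% against 5%, a factor of about 1.7.

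**Lognormality.** With baseline and Day 1 drawn from the same gamma distribution (ratio CV about 0.56), the false-increase rate is 7.2%.

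**The fallback.** The plan gives no trigger, so one has to be assumed. At CV 0.6:

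- Switching to logs when a Shapiro-Wilk test rejects at 5%: the check detects the skew in 51% of trials, and the false-increase rate is 6.6%.
- A Wilcoxon test on raw fold-change minus 1: 5.4%, because this quantity is also not symmetric about 0.

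**The case against.** **The CV.** The figure of 0.6 pools treated responders and non-responders, so it includes differences in drug response. Untreated within-patient variability is the relevant quantity, and the documents do not give it. At CV 0.1 the false-increase rate is only 3.2%. This stands as a limit on the size of the error, not on its existence.

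**The nominal rate.** The plan's test is two-tailed, and against the total of 5% the inflation is 1.7-fold at CV 0.6. That figure belongs alongside the other, but 2.5% is the right reference for falsely declaring an increase.

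**The null.** The plan's target is the arithmetic mean. If that mean were truly 1, the raw test would reject upward only 0.6% of the time. However, interchangeable baseline and Day 1 values do not give an arithmetic mean of 1, so that null does not describe the absence of an effect.

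**The fallback.** Results depend on the trigger: a Shapiro-Wilk test at 10% leaves 5.5%, and switching when sample skewness exceeds 0.5 (81% of trials) leaves 4.2%. Each rule reduces the inflation and none removes it. The modelled switch lowers the error; extra inflation from choosing freely among the three tests is possible but was not quantified.

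**Practical weight.** The bias is at most 1.17 at the documented CVs, against a planned effect of 1.7 and a reported mean of 2.5 even in non-durable responders. A large true effect would probably be declared by either test. The risk concerns a null or near-null result, which is the case a significance test is meant to guard against.

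**Conclusion.** The concern holds. As written, the primary Ki67 test does not keep its error rate when baseline and Day 1 values are interchangeable. At n = 17 it falsely declares an increase in about 5% to 8% of trials for CVs of 0.3 to 0.6, or two to about three times the nominal 2.5%. The optional fallback does not repair this under any of the trigger rules tried; the log-scale test does.

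The size rests on two assumptions: approximately lognormal ratios, and a null CV in that range. A smaller null CV gives less inflation. Three times is not a ceiling: if all 20 patients gave data at CV 0.6, the rate would be 10.1%, or four times nominal.

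**What to change.** In section 15.5.2.2, make the primary analysis a one-sample t-test of log(Day 1 Ki67 / baseline Ki67) against 0, two-sided at 0.05. Report the geometric mean fold-change with a back-transformed 95% confidence interval. Name a Wilcoxon signed-rank test on the log ratios as a sensitivity analysis, and delete the choice of method after the data are seen.

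Match the wording in sections 5.6 and 8, and state in section 15.8 that 1.7 is a geometric mean.

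The cost is a few sentences, with no new data and no more patients. The effect measure becomes the geometric mean ratio. Power is then 95.9% with 17 patients. If 1.7 was meant as an arithmetic mean, the geometric mean at CV 0.6 is 1.7/1.166 = 1.46 and log-scale power is 74.9%, so the sponsor needs to say which was intended.

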#### **15.5.2.3. Additional Analyses**

Ki67 from circulating PD-1/CD8+ T cells at Day 1 will be correlated to intratumoral PD-1/CD8+ T cells based on nonparametric correlation, Spearman's rank order correlation.

### **15.6. Exploratory Objectives**

This study has several exploratory objectives including the description of survival, time to local intracranial progression, time to distant intracranial progression, time to overall intracranial progression, and progression-free survival. The rate of radionecrosis will also be explored, as immune expression profiles.

Some of the proposed exploratory analyses may generate p-values. If they do, they will be viewed as descriptive and exploratory in nature.

### **15.6.1. Exploratory Objective #1: Survival**

Survival is defined as the time between initiation of checkpoint treatment and death; survival time will be censored if the patient remained alive at the time of last follow-up. A Kaplan-Meier estimator will describe the survival of patients and associated survival statistics (e.g. median survival, survival at 6 months, 12 months, and 18 months) will be estimated.

In addition, exploratory analyses will assess the impact of fold-change in T-cell proliferation (KI-67) between baseline and Day 1 on subsequent survival, using a Cox model with fold-change as predictors of survival post-surgery.

### **15.6.2. Exploratory Objectives #2 - #5: Disease Progression**

Several different efficacy measures of progression will be computed as part of exploratory objectives #2 - #5:

- The time to local intracranial progression is the time between initiation of checkpoint treatment and first identification of local intracranial progression, which is defined by RANO-BM criteria. If a patient experiences a distant intracranial progression or dies before documentation of local progression, the time to local intracranial progression will be censored at the time of distant intracranial progression or the time of death.
- The time to distant intracranial progression is the time between initiation of checkpoint treatment and first identification of distant intracranial progression, which is defined by RANO-BM disease progression criteria. If a patient locally progresses intracranially or dies before documentation of distant intracranial progression, the time to distant intracranial progression will be censored at the time of local intracranial progression or the time of death.
- The time to overall intracranial progression is the time between initiation of checkpoint treatment and first identification of intracranial progression (distant or local), as defined by RANO-BM criteria. If a patient dies before documentation of intracranial progression, the time to overall intracranial progression will be censored at the time of death.

- Progression-free survival is the time between initiation of checkpoint treatment and first progression (intracranial or extracranial), or death if the patient dies without documented disease progression, as defined by RECIST 1.1. If the patient remains alive without disease progression at the time of analysis, progression-free survival will be censored at the time of last follow-up.

Given that death, local intracranial recurrence, and distant intracranial recurrence are competing events, time to local intracranial recurrence, time to distant intracranial recurrence, and time to overall intracranial recurrence will be graphically described using a cumulative incidence function.

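### Section 15.6.2 censors three exploratory intracranial progression times at events it also calls competing; coded that way, the curves and the Section 8 medians would not be those of the planned cumulative incidence function

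*Combined protocol and SAP*

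**What the plan says.** Section 15.6.2 defines three intracranial progression times, all starting at the first checkpoint treatment.

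- Local: "the time to local intracranial progression will be censored at the time of distant intracranial progression or the time of death".
- Distant: "the time to distant intracranial progression will be censored at the time of local intracranial progression or the time of death".
- Overall (local or distant): "the time to overall intracranial progression will be censored at the time of death".

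The closing paragraph of the same section begins "Given that death, local intracranial recurrence, and distant intracranial recurrence are competing events" and plans to describe all three times graphically with a CIF. The synopsis agrees. In Section 5.6, "cumulative incidence curves will be used to graphically display time to local intracranial progression", with the distant and overall times in the same sentence, and Kaplan-Meier is named only for survival and progression-free survival (PFS).

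Section 8 makes a median the endpoint for each time: "Median time to local intracranial progression", "Median time to distant intracranial progression", and likewise for overall intracranial progression. It refers to Section 15.6.2 for the analysis, but that section mentions no median for these times. By contrast, Section 15.6.1 ties median survival to a Kaplan-Meier estimator.

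**The concern.** One patient event is given two incompatible codes. A CIF with competing events needs to know that a patient left the risk set through distant progression or death. Censoring removes that information and treats the patient as someone who could still have had the event later.

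Three things are at stake if a dataset is built from the definitions:

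1. Each curve becomes 1 minus Kaplan-Meier.
2. Local and distant incidence no longer add up to overall incidence.
3. A median can be reported for a time whose CIF never reaches 50%. Section 8 asks for medians, and a time defined with censoring most naturally leads an analyst to a Kaplan-Meier median.

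**Working it through.** The plan states no figure for these times, so there is none to reproduce. The check is why the coding matters and how large the effect could be.

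**Why the curves differ.** At each event time the CIF rises by S(t−) × d/n, where d is the number of target events, n the number at risk, and S the probability of being free of every event type. If competing events are coded as censored, S becomes the Kaplan-Meier curve for the target event alone. That curve is never below the all-event S, so every step is at least as large. The result, 1 − KM, is at or above the CIF from the same data. This ordering holds for one dataset. It does not say that an estimate from 20 patients must exceed the true incidence.

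**Inputs.**
- Follow-up of 18 months (Section 9.1).
- Median survival of around 10.8 months (Section 7.1), used as an approximate constant hazard of death: ln 2/10.8 = 0.0642 per month.
- Local and distant progression: no rates in the documents. Assumed cause-specific median of 12 months each: ln 2/12 = 0.0578 per month.

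**Formulas**, with λ the target hazard and Λ the sum over all event types:
- Censored coding: 1 − exp(−λt)
- CIF: (λ/Λ)(1 − exp(−Λt))
- Median under censored coding: ln 2/λ
- CIF median: −ln(1 − 0.5Λ/λ)/Λ, which exists only if λ/Λ exceeds 0.5

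**Anchored case, t = 18.** Λ = 0.0578 + 0.0578 + 0.0642 = 0.1797 (from unrounded hazards), and 1 − exp(−0.1797 × 18) = 0.961.

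| | Censored coding | CIF | Median, censored | Median, CIF |
|---|---|---|---|---|
| Local | 1 − exp(−0.0578 × 18) = 64.6% | 0.321 × 0.961 = 30.9% | 12.0 months | never (plateau 32.1%) |
| Distant | 64.6% | 30.9% | 12.0 months | never (plateau 32.1%) |
| Overall | 1 − exp(−0.1155 × 18) = 87.5% | 0.643 × 0.961 = 61.8% | 6.0 months | 8.4 months |

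The CIF values add up: 30.9 + 30.9 = 61.8. The censored-coding values sum to 64.6 + 64.6 = 129.2%, against 87.5% overall.

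**Other assumed progression rates, same death hazard.** Over six pairs of medians (local 8 to 36 months, distant 8 to 24 months), the ranges at 18 months are:
- Local: 29–79% censored against 11–46% CIF.
- Distant: 41–79% against 15–49%.
- Overall: 79–93% against 54–68%.

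No local or distant CIF reaches 50% within 18 months in any of the six.

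**Low case.** Hazards of 0.005/0.01/0.005 per month for local/distant/death give 8.6% against 7.6% (local), 16.5% against 15.1% (distant) and 23.7% against 22.7% (overall). The gaps are about 1 point, and neither coding is expected to reach a median by 18 months. This death hazard implies a median of ln 2/0.005 = 139 months, far above Section 7.1's figure, so it serves as a lower limit.

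**Hypothetical 20-patient count.** All are followed for 18 months. First events are distant 7, local 3, death 4, none 6. The CIF at 18 months is 3/20 = 15.0% local, 7/20 = 35.0% distant and 10/20 = 50.0% overall, whatever the order. Take the order (distant, death, distant, local) three times, then distant, then death:
- Local, censored coding: 1 − (16/17)(12/13)(8/9) = 22.8%
- Distant: 1 − (19/20)(17/18)(15/16)(13/14)(11/12)(9/10)(7/8) = 43.6%
- Overall: 1 − (1 − 0.228)(1 − 0.436) = 56.5%

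Censored coding therefore crosses 50% earlier for overall progression, and 22.8 + 43.6 = 66.4 does not equal 56.5.

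**The case against.** The strongest reply is that the section must be read whole. The definitions say when each clock stops, and the closing paragraph says how the data are described. The CIF is named both there and in the synopsis, and Kaplan-Meier is kept for survival and PFS. On that reading, 1 − KM appears only if an analyst overlooks the named method. This stands for the plots. A reader might infer that the planned CIF analysis is itself wrong, or that the plan prescribes Kaplan-Meier for these times. The documents support neither.

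The reply does not remove the point. The definitions state a coding rule that conflicts with the method, and the CIF is named only for graphs, while the endpoints are medians. Censoring competing events is proper for cause-specific hazards, but no such analysis of these times is planned.

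A second reply is that median PFS also has no estimator tied to it in Section 15.6.2. That is true, and one sentence settles it. PFS counts death as an event, and the only curve named for it is Kaplan-Meier, so the coding conflict does not arise there.

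A third is that the size rests on assumptions. That also stands. Overall survival includes deaths after intracranial progression, so 10.8 months is only a rough guide to death as a first event. The local and distant figures also take first-event incidence as the target, which fits the section calling the two competing. If only death competed and hazards were unchanged after the other progression type, the anchored local CIF would be (0.0578/0.1219)(1 − exp(−0.1219 × 18)) = 42.1%, still well below 64.6%. The overall gap does not depend on this choice.

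**Conclusion.** The three definitions are wrong as written, because they conflict with the closing paragraph of their own section, and the Section 8 medians have no stated estimator to settle which reading applies. Followed literally, they overstate the three summaries relative to the plan's own CIF from the same data. The illustrative 18-month gaps run from about 1 point under low assumed hazards to 33.7 points (local and distant) and 25.7 points (overall) in the anchored case. The progression hazards are assumed, constant hazards are assumed, and the death hazard is approximated from a background survival figure.

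Severity is minor. Only exploratory objectives #2 to #4 are affected. They are descriptive, in up to 20 patients, and no primary objective, test or stopping rule depends on them. It would be too strong to infer that the survival or PFS results are biased: neither is censored at a competing event.

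**What to change.** 1. In the three definitions in Section 15.6.2, say that the other progression type or death is treated as a competing event at that time, instead of as censoring.
2. Record each patient's first event with a type code: local, distant or death.
3. State in Sections 15.6.2 and 8 that any median for these three times is the time at which the CIF reaches 50%, and otherwise is reported as not reached.
4. For consistency, state that median PFS is read from the Kaplan-Meier curve already named in Section 5.6.

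While the text is open, the last-follow-up rule that PFS has ("progression-free survival will be censored at the time of last follow-up") can be written for patients alive without intracranial progression. That is missing detail with an obvious default, not a separate error.

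The cost is a few sentences and the event coding, with the same data, visits and plots. The downside is that some local and distant medians may be reported as not reached.
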